5.0 DOSE MODIFICATION FOR TOXICITY

5.1 Dose Limiting Toxicity (DLT)

A DLT is defined as a clinically significant adverse event or abnormal laboratory value assessed as unrelated to disease progression, intercurrent illness, or concomitant medications and meets any of the criteria below. Any DLT must be a toxicity considered at least possibly related to pamiparib (BGB-290) or TMZ.

ABTC # 1801

NCI # ABTC-1801

PI: [name]

Dose limiting toxicities (treatment related) are defined below. Dose limiting toxicities must have an attribution of possible, probable, or definite to pamiparib (BGB-290) or TMZ. For patients experiencing a DLT, pamiparib (BGB-290) and TMZ will be stopped. If the patient recovers (\leq grade 1 [or tolerable grade 2 for non-hematologic toxicity] or \leq baseline), refer to the Toxicity Management Table below for instruction on whether a dose reduction of TMZ or pamiparib (BGB-290) is required for subsequent doses, or whether pamiparib (BGB-290) and TMZ must be permanently discontinued. Skipped doses will not be made up. If there is any question or confusion concerning a DLT, the treating site should contact the ABTC Central Office to determine patient's DLT status. The ABTC Central Office, with the Study Chair, will make the final decision.

- → Hematological toxicities will be considered dose limiting if any of the following occur and complete blood counts and differentials were obtained according to the mandated schedule (CBC, differential, and platelets drawn twice a week until the ANC ≥ $1500/\mu$ L and platelets ≥100,000/µL): grade 3 or 4 lymphopenia will not be considered a DLT.
 - Grade 4 Neutrophil count decreased (ANC of $< 500/\mu$ L)
 - Grade 4 Platelet count decreased (Platelets $< 25,000/\mu$ L)
 - Grade 3 or 4 Febrile neutropenia
 - Any hematological toxicity that prevents administration of > 80% of the planned TMZ doses for the first cycle

Non-hematological toxicities will be considered dose limiting if any of the following occur:

- Grades 3-4 seizure or intracranial hemorrhage
 - All other grade 3 neurologic toxicity (other than seizure/intracranial hemorrhage) responding *within 3 days* to steroids, anticonvulsants, or electrolyte correction will not be considered dose limiting.
- Grades 3-4 severity with the following exceptions:
 - o except nausea, vomiting, and diarrhea without sufficient prophylaxis *lasting* ≤3 *days*;
 - except alopecia;
 - except grade 3 hyperglycemia;

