5.2.1 Dose Modification for Temozolomide and Pamiparib (BGB-290)

Dose reductions are required as indicated in the toxicity table above for any dose limiting toxicity (as defined in Section 5.1). Dosing will stop until the DLT has resolved to \leq grade 1 [or tolerable grade 2 for non-hematologic toxicity] or \leq baseline. The maximum length of time that pamiparib (BGB-290) and TMZ can be held is 21 days, or as stipulated in the table. After resolution, the dose of TMZ will be modified as stipulated below, with a maximum of 2 dose reductions. If treatment-related toxicity is not resolved in \leq 21 days (or as stipulated), the patient will be considered for monotherapy with pamiparib (BGB-290). If there is any question, the ABTC Central Office and the study chair should be contacted.

Dose level	Temozolomide dose	Dose reduction 1	Dose reduction 2
1 (starting dose)	20 mg QD Days 1-28	20 mg QD Days 1-21	20 mg QD Days 1- 14
-1	20 mg QD Days 1-21	20 mg QD Days 1-14	20 mg QD Days 1-7
-2	20 mg QD Days 1-14	20 mg QD Days 1-7	Either off study or pamiparib (BGB- 290) alone
-3	20 mg QD Days 1-7	Either off study or pamiparib (BGB-290) alone	N/A

TMZ Dose Reduction Schedule

ABTC # 1801

Blood counts will be evaluated weekly. Within -5 days prior to first dose of each cycle the patient must have an ANC \geq 1500/ul and platelet count \geq 100,000/ul. On Day 1 of each cycle (within -5 days) all **non-hematological** toxicity grade 3 or 4 (except for alopecia, nausea and vomiting) must have resolved (CTCAE grade \leq 1). If toxicity persists, treatment should be delayed by one week for up to 3 consecutive weeks. If after 3 weeks of delay all toxicity has still not resolved then any further treatment with temozolomide should be stopped (patient is off treatment).

If pamiparib (BGB-290) must be modified as stipulated in the Toxicity Management Table, the dose of pamiparib (BGB-290) will be modified as shown below, with a maximum of 2 dose reductions.

PI: [name]

NCI # ABTC-1801

PI: [name]

Dose Level	Pamiparib (BGB-290)					
Starting dose	60 mg b.i.d.					
First dose reduction	40 mg b.i.d.					
Second dose reduction	20 mg b.i.d.					

Pamiparib (BGB-290) Dose Reduction Schedule

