9– If ANC < 1500 or plts < 100,000, CBCs/differentials will be repeated twice a week until counts are recovered (ANC ≥1500 or plts ≥100,000) per protocol. If counts are recovered (ANC ≥1500 or plts ≥100,000) on day of scheduled drawing do not repeat until next protocol schedule day

10 - Adverse Events must be followed for at least 30 days from last dose of pamiparib (BGB-290).

11-Perform within +14 days of the 30-day post-last dose date.

12– Archived tumor tissue from a prior resection for glioma, preferably from the initial diagnosis, will be collected from all patients. See Section 9.5.1.

 $13\!-\!\pm 1~day$

14-Perform within minus 7 days of first dose

ABTC # 1801

NCI # ABTC-1801

PI: [name]

15- In subjects whose CBC, Diff, Platelets have been stable through the first 6 cycles, the frequency of hematologic testing can be reduced to a q2 weeks schedule (Day 15 of every cycle and Pre-cycle evaluation) starting in Cycle 7. CBC, Diff, Platelets will be considered "stable" if the following criteria are met: 1) No reports of ANC<1500/µl in ANY of the Cycles 1-6 weekly Labs and 2) No reports of Platelets<100,000/µl in ANY of the Cycles 1-6 weekly Labs and 2) No reports of Platelets<100,000/µl in ANY of the Cycles 1-6 weekly Labs. If at any point during treatment on the revised q2 weeks schedule the above mentioned ANC and Platelets criteria are not met, CBC, Diff, Platelets should be repeated twice a week until counts are recovered (ANC ≥1500 or Platelets ≥100,000). Once counts are recovered, the schedule of CBC, Diff, Platelets should go back to, and stay at, weekly monitoring (NOT q2 weeks).

IMPORTANT: The guidance below is subject to applicable local Institutional Policy on telemedicine. In the event that local Institutional Policy regarding telemedicine differs from this guidance, then please follow local Institutional Policy.

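### Four schedule-table footnotes let twice-weekly blood counts stop when ANC 'or' platelets is adequate, whereas Section 5.1 requires both

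*Combined protocol and SAP*

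**What the plan says.** **Footnote 9, in both 9.1.1 and 9.1.2.** The trigger is either count being low: "If ANC < 1500 or plts < 100,000, CBCs/differentials will be repeated twice a week". The draws continue "until counts are recovered (ANC ≥1500 or plts ≥100,000) per protocol". A second sentence repeats the same 'or' definition and says of a patient who meets it: "on day of scheduled drawing do not repeat until next protocol schedule day".

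**Footnote 15 of 9.1.1 and footnote 19 of 9.1.2.** These apply from Cycle 7 to patients moved to two-weekly counts. If either count then falls below its limit, counts "should be repeated twice a week until counts are recovered (ANC ≥1500 or Platelets ≥100,000"; after that, "Once counts are recovered, the schedule of CBC, Diff, Platelets should go back to, and stay at, weekly monitoring". Neither footnote contains the words 'per protocol' that appear in footnote 9.

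**Section 5.1.** A hematologic toxicity is scored as dose limiting if a listed event occurs and "complete blood counts and differentials were obtained according to the mandated schedule". The parenthesis that follows defines the schedule: "CBC, differential, and platelets drawn twice a week until the ANC" is at least 1500 and platelets are at least 100,000. The connective there is 'and'.

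**Other count rules.** The pre-cycle requirements in Sections 4.4, 4.5.2 and 5.2.1 also join the two counts with 'and'. Section 5.2.1 keeps a weekly minimum: "Blood counts will be evaluated weekly".

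**The concern.** A stop rule for extra monitoring should be the opposite of the rule that starts it. Here both are written with 'or', so they overlap, and a patient can satisfy start and stop on the same blood draw. Section 5.1 and the observation tables then give sites two different schedules for the same patient.

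Two things are at stake. First, safety observation: between weekly draws, a count that is already low could fall briefly to grade 4 (ANC below 500 or platelets below 25,000 in Section 5.1) and come back unseen. Second, DLT scoring: Section 5.1 ties it to counts having been drawn on its own schedule, so a site following footnote 9 in Cycle 1 of Phase I departs from that condition. Hematologic toxicity is the relevant risk. Section 2.2 reports that pamiparib 60 mg twice daily with TMZ 40 mg exceeded the MTD because of neutropenia and thrombocytopenia in one study, and caused excessive hematologic toxicity in another. This trial uses TMZ 20 mg, so those findings show the kind of risk but not its size here.

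**Working it through.** The plan states no figure on this point to reproduce. The check is one of logic, followed by a count of draws.

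**Step 1. Trigger against stop rule.** Write A for ANC and P for platelets.

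- Trigger (footnote 9): A < 1500 or P < 100,000.
- Logical opposite of the trigger: A ≥ 1500 and P ≥ 100,000. This is the Section 5.1 rule.
- Stop rule in the footnotes: A ≥ 1500 or P ≥ 100,000.

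| State | Trigger met | Recovered under the footnotes | Recovered under 5.1 |
|---|---|---|---|
| Both adequate | no | yes | yes |
| ANC low only (e.g. 800, with platelets 150,000) | yes | yes | no |
| Platelets low only | yes | yes | no |
| Both low | yes | no | no |

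In 2 of the 3 triggering states the footnotes' recovery condition already holds on the triggering draw, so the repeats need never start. In the third state they stop when the first of the two counts recovers, because the patient has then moved into one of the two middle rows.

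**Step 2. Number of draws, as an illustration.** Assume weekly draws on Days 8, 15 and 22 of Cycle 1, and one count low from Day 8 to the end of the cycle. The protocol does not fix the spacing of the second weekly draw, so let it fall k days after the first, with k from 2 to 5.

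- Section 5.1: one extra draw after each weekly draw, on Days 8+k, 15+k and 22+k. With k = 3 these are Days 11, 18 and 25. The latest possible day is 22 + 5 = 27, still inside the 28-day cycle. Extra draws: 3 for every k in the range.
- Footnote 9, read literally: 0 extra draws.

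**Step 3. Where DLT scoring can be touched.** Section 4.1.1 limits the toxicity evaluation period to the first 4 weeks.

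- Footnotes 15 and 19 act only from Cycle 7, so they fall outside it.
- The Surgical Portion (9.1.2) opens after Phase I is complete (Section 4.3), so neither of its footnotes bears on dose finding.
- This leaves footnote 9 of 9.1.1, in Cycle 1 of Phase I.

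**Step 4. Effect of the correction.** With 'and' in the recovery parentheses, the stop rule becomes the exact opposite of the trigger. Draws continue in all three low-count rows and stop only in the first row, as in Section 5.1.

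**The case against.** The strongest reply is that no sensible site would follow a rule that cancels itself. The parenthesis mirrors the trigger, and the natural reading of 'or' is 'whichever count was low', which agrees with Section 5.1. Footnote 9 also says 'per protocol', which can be taken as deferring to 5.1. Questions about DLT status go to the Central Office, which decides with the Study Chair.

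Much of this stands. The wording is probably a drafting slip, and some sites will do what was meant. Harm arises only where a site follows the literal footnote over Section 5.1. But the charitable reading does not remove the conflict. Footnote 9 goes on to tell sites not to redraw once the patient is 'recovered'. Footnotes 15 and 19 have no 'per protocol' and send the patient to weekly draws. Site staff may well work from the observation table, and they should not have to choose between readings of a safety schedule.

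A reader might infer that the footnotes allow dosing while a count is low. They do not. The Toxicity Management Table in Section 5.2 holds both drugs for grade 3 or 4 neutropenia or thrombocytopenia until that count recovers, and every pre-cycle threshold requires both counts. A reader might also infer a measurable distortion of the table's 7-day recovery rule. That would depend on the spacing of midweek draws, which the protocol does not set, so no figure is offered.

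**Conclusion.** Wrong as written, low severity. This is an internal inconsistency in safety monitoring, not a design choice. The textual conflict is certain: six recovery parentheses in four footnotes say 'or', while Section 5.1 and every pre-cycle criterion say 'and'.

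The consequence is limited to how often blood is drawn after a low count has been found. In the illustration it is 3 extra draws against 0 in Cycle 1, given the assumed weekly days, one count low from Day 8 onward, and a site that follows the footnote literally. Such a site may miss a short grade 4 fall and departs from the schedule to which Section 5.1 ties DLT scoring.

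It is tempting to go further and say that the observed DLT rate or the selected MTD is biased, since in the 3+3 design 2 of 6 is the MTD and 3 of 6 exceeds it. The documents do not support that. They give neither the frequency of isolated low counts nor the duration of grade 4 falls, so no probability of a missed DLT can be derived. Sample size, power and error rates for Phase II are unaffected.

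**What to change.** Replace 'or' with 'and' in the six recovery parentheses: two in footnote 9 and one in footnote 15 of Section 9.1.1, and two in footnote 9 and one in footnote 19 of Section 9.1.2. Leave the 'or' in the footnote 9 trigger as it is, since either low count should start the extra draws.

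The cost is one word in six places. In Cycle 1 of Phase I the change adds no draws beyond those Section 5.1 already requires. In later cycles and in the Surgical Portion it adds draws only relative to the literal reading, and only while a count remains low.

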	Second and subsequent occurrences: hold pamiparib (BGB-290) and TMZ until resolved to \leq Grade 1 or baseline:
	-if resolved \leq 14 days, then maintain dose levels
	-if resolved > 14 days, then ↓ TMZ by 1 dose level and continue pamiparib (BGB-290) at same dose
Grade 3 Anemia (Hb < 8 g/dL)	Hold pamiparib (BGB-290) and TMZ until resolved to Grade ≤ 1 or baseline
	-if resolved \leq 7 days, then maintain dose levels
	-if resolved > 7 days, then decrease TMZ by 1 dose level

NCI # ABTC-1801

Toxicity	Actions
Grade 4 Anemia (life threatening consequences; urgent intervention indicated)	Hold pamiparib (BGB-290) and TMZ until resolved to Grade ≤ 1 or baseline and
	decrease TMZ by 1 dose level

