- 13– Blood samples will be obtained for pharmacokinetics at baseline (prior to first pre-surgical dose), and shortly before and after surgical resection. Section 9.5.2.
- 14-Fresh tumor tissue for drug concentration will be collected day of surgery. See Sections 9.5.2.
- 15- Patient should be seen on the day of surgery (prior to surgery) to evaluate for AEs.
- 16– Within 3 days post-surgery.
- 17- Perform within minus 7 days of first dose.
- 18-± 1 day
- 19- In subjects whose CBC, Diff, Platelets have been stable through the first 6 cycles, the frequency of hematologic testing can be reduced to a q2 weeks schedule (Day 15 of every cycle and Pre-cycle evaluation) starting in Cycle 7. CBC, Diff, Platelets will be considered "stable" if the following criteria are met: 1) No reports of ANC<1500/µl in ANY of the Cycles 1-6 weekly Labs and 2) No reports of Platelets<100,000/µl in ANY of the Cycles 1-6 weekly Labs. If at any point during treatment on the revised q2 weeks schedule the above mentioned ANC and Platelets criteria are not met, CBC, Diff, Platelets should be repeated twice a week until counts are recovered (ANC ≥1500 or Platelets ≥100,000). Once counts are recovered, the schedule of CBC, Diff, Platelets should go back to, and stay at, weekly monitoring (NOT q2 weeks).

IMPORTANT: The guidance below is subject to applicable local Institutional Policy on telemedicine. In the event that local Institutional Policy regarding telemedicine differs from this guidance, then please follow local Institutional Policy.

Telemedicine visits may be substituted for in person clinical trial visits or portions of clinical trial visits where determined to be appropriate and where determined by the investigator not to increase the participants risks. Prior to initiating telemedicine for study visits the study team will explain to the participant, what a telemedicine visit entails and confirm that the study participant is in agreement and able to proceed with this method. Telemedicine acknowledgement will be obtained in accordance with the Guidance for Use of Telemedicine in Research. In the event telemedicine is not deemed feasible, the study visit will proceed as an in-person visit. Telemedicine visits will be conducted using HIPAA compliant method approved by the Health System and within licensing restrictions.

Additionally, informed consent should be obtained in person, but if deemed necessary, via telemedicine.

ABTC # 1801

NCI # ABTC-1801

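### From Cycle 7, blood counts can drop to every two weeks on ANC and platelet stability alone, so a patient already held or TMZ-reduced for anemia qualifies and is not returned to weekly counts if it recurs

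*Combined protocol and SAP*

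**What the plan says.** **Reduced schedule.** Footnote 15 (Section 9.1.1) and footnote 19 (Section 9.1.2) carry the same rule. Starting in Cycle 7, for patients whose counts were stable through six cycles, footnote 15 says that "the frequency of hematologic testing can be reduced to a q2 weeks schedule (Day 15 of every cycle and Pre-cycle evaluation". Footnote 19 likewise says that "the frequency of hematologic testing can be reduced to a q2 weeks schedule", on the same days. Counts "will be considered 'stable' if the following criteria are met", and two criteria follow: no ANC below 1,500/µl and no platelets below 100,000/µl in any weekly lab of Cycles 1-6.

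**Way back.** If "at any point during treatment on the revised q2 weeks schedule the above mentioned ANC and Platelets criteria are not met", counts are repeated twice a week until they recover. After that the schedule "should go back to, and stay at, weekly monitoring". Hemoglobin appears in neither the definition nor this trigger.

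**Footnote 9.** When ANC or platelets fall below the same limits, "CBCs/differentials will be repeated twice a week until counts are recovered". Hemoglobin is not named here either, and this applies from Cycle 1.

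**Dose modification.** The Toxicity Management Table in Section 5.2 acts on anemia at three levels:
- Grade 2: dosing continues at the first episode. The rule then becomes "Second and subsequent occurrences: hold pamiparib (BGB-290) and TMZ until resolved", with a TMZ reduction if recovery takes more than 14 days.
- Grade 3: both drugs are held, and "if resolved > 7 days, then decrease TMZ by 1 dose level".
- Grade 4: both drugs are held and TMZ is reduced by one level.

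**Related text.** Section 4.4 requires hematologic toxicity to be back to grade 1 or baseline before every cycle. Sections 4.5.2 and 5.2.1 both call for weekly counts and mention no exception from Cycle 7. Section 9.2.1.2 lists anemia among the known toxicities of TMZ.

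**The concern.** The footnotes are meant to lighten monitoring only for patients whose blood counts have given no trouble, and to restore it when they do. Section 5.2 treats hemoglobin as a count that can stop both drugs and lower TMZ, yet the footnotes leave it out. A single platelet value of 99,000/µl in Cycles 1-6 bars a patient from the lighter schedule, while a hemoglobin below 8 g/dL that led to a hold does not.

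What is at stake is how soon a recurrence is found in patients who have already shown that they become anemic on this combination. In the Section 9.1 tables the CBC is the only scheduled mid-cycle assessment; AE evaluation, examination and chemistry fall before each cycle. The follow-up of abnormal results in Section 9.2.2 begins only once an abnormality is known. While the recurrence is unseen, both drugs continue.

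**Working it through.** The plan states no figure to reproduce. The check has two parts: who qualifies, and how far apart the required counts are.

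**Inputs**
- Stability criteria: ANC and platelets, footnotes 15 and 19.
- Pre-cycle draw: within 5 days before cycle start (footnote 5 in both tables). With cycle start as Day 1 and Day 0 counted, this is Days -4 to 1, and Days 24 to 29 for the next cycle.
- In-cycle draws: plus or minus 1 day (footnote 13 in 9.1.1, footnote 18 in 9.1.2).
- Cycle start: up to 3 days late (Section 4.5.2).
- Assumption: weekly draws fall on Days 8, 15 and 22. The tables say only that they are weekly.

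**Step 1: who qualifies.** Take a patient with ANC 2,000/µl and platelets 150,000/µl throughout Cycles 1-6. Both criteria are met whether the hemoglobin is 11, 9.5, 7.5 or 6 g/dL. Under Section 5.2, the 7.5 g/dL value means a hold of both drugs, with a TMZ reduction if recovery takes more than 7 days. The same logic applies after Cycle 7: a recurrence at any of these values does not trip the return to weekly.

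**Step 2: counts per cycle.** Weekly: pre-cycle, Days 8, 15 and 22 = 4. Reduced: pre-cycle and Day 15 = 2.

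**Step 3: days between required counts**

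| Interval | Weekly | Every two weeks |
|---|---|---|
| From pre-cycle draw, nominal | 8 - 1 = 7 | 15 - 1 = 14 |
| From pre-cycle draw, shortest with windows | 7 - 1 = 6 | 14 - 1 = 13 |
| From pre-cycle draw, longest with windows | 9 - (-4) = 13 | 16 - (-4) = 20 |
| From Day 15, nominal | 22 - 15 = 7 | 29 - 15 = 14 |
| From Day 15, shortest with windows | 21 - 16 = 5 | 24 - 16 = 8 |
| From Day 15, longest with windows | 23 - 14 = 9 | 29 - 14 = 15 |

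If the next cycle starts 3 days late (Day 32), the longest gap from Day 15 on the reduced schedule is 32 - 14 = 18 days.

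**Step 4: what this means for detection.** A recurrence that would first have shown on Day 8 is found on Day 15 (15 - 8 = 7 days later). One that would first have shown on Day 22 is found at the next pre-cycle draw (nominally 29 - 22 = 7 days later). One that first shows on Day 15 or pre-cycle is found at the same time under either schedule. The nominal delay is therefore either nothing or one week.

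**The case against.** The case for leaving the text alone has real substance.

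- **The Section 4.4 requirement.** Anemia must have recovered to grade 1 or baseline before Cycle 7 and each later cycle. A reader might infer that the footnotes let an anemic patient keep being treated; they do not. The exposure is to a fall that begins after the pre-cycle draw. This stands, and it limits the point to recurrence within a cycle.
- **Hemoglobin is still measured.** Every remaining CBC includes it. A reader might infer that anemia goes unmonitored from Cycle 7. The documents support later detection only.
- **The option is permissive.** A site may stay on weekly counts, and Sections 4.5.2 and 5.2.1 still call for them. This stands, but silence on the exception does not supply a hemoglobin rule; it leaves body text and footnotes inconsistent.
- **The focus on ANC and platelets is consistent.** The numeric pre-cycle thresholds, the DLT count thresholds and footnote 9 also name only these two, and a first grade 2 anemia continues at full dose. That suggests a deliberate choice for mild anemia. It does not explain why a patient whose anemia did lead to a hold or reduction should count as stable.
- **Grade 4 adds little.** It is defined by life-threatening consequences and would present clinically. The point rests on repeat grade 2 and on grade 3.
- **The opening of the footnote refers to the CBC as a whole.** This might be read to include hemoglobin, but the explicit definition that follows is limited to ANC and platelets.

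A reader might also infer that the 7-day cut for grade 3 anemia becomes unworkable. That goes too far. Once anemia is known, the hold and Section 9.2.2 make an unscheduled CBC likely. Bilirubin and creatinine have the same 7-day cut with chemistry scheduled only pre-cycle.

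**Conclusion.** The point holds, as a minor patient-safety matter. As written, the footnotes admit a patient with an anemia-related hold or TMZ reduction in Cycles 1-6 to counts every two weeks, and do not send that patient back to weekly if anemia recurs. The cost is a recurrence found up to about a week later. The nominal gap is 14 days instead of 7, and at worst 20 instead of 13 from the pre-cycle draw. These gaps rest on the Day 8, 15 and 22 grid and the stated windows.

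The affected group is small: it needs treatment into Cycle 7, a site that uses the option, and anemia with ANC and platelets above the limits. The documents give no frequency for it. No trial conclusion is affected: the DLT period is Cycle 1, the primary endpoint is radiographic response, and the operating characteristics do not depend on the count schedule.

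**What to change.** In footnotes 15 and 19:
- add to the stability criteria: *no anemia requiring a hold or TMZ reduction under Section 5.2 in Cycles 1-6*;
- make the same kind of anemia, if it occurs on the reduced schedule, a trigger for return to weekly counts.

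In Sections 4.5.2 and 5.2.1, state the Cycle 7 exception with a cross-reference, so that body text and tables agree.

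Leave footnote 9 as it is. Extending its twice-weekly repeats to anemia holds would apply from Cycle 1 in every portion of the study. With holds allowed for up to 21 days, that could mean about 6 draws per episode (3 weeks x 2), which goes beyond this gap.

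The cost is a wording change in two footnotes and two cross-references. For affected patients it is 2 further scheduled CBCs per cycle compared with the reduced schedule (4 - 2), in a small group.
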